**List of Abbreviations**

AMD – Age related macular degeneration  
FDA – Food and drug administration  
IOP – Intraocular Pressure  
NYU – New York University  
OCT – Optical coherence tomography  
ODM- Ophthalmodynamometer  
ONH – Optic Nerve Head  
ORA – Ocular Response Analyzer  
UPMC – University of Pittsburgh medical center  
VF – Visual field

## Keratoconus and IOP Elevation Study

### Study Summary

Title	Optic Nerve Head Structural Response to IOP Elevation in Patients with Keratoconus
Short Title	Keratoconus and IOP elevation Study
IRB Number	17-01360
Study Type	Human study
Study Design	Prospective experimental study
Study Intervention	In-vivo investigation of ocular structure in eyes with keratoconus under elevated intraocular pressure
Study Duration	Indefinite
Study Location(s)	NYU Department of Ophthalmology: Faculty Group Practice
Primary Objective	To examine in-vivo how lamina cribrosa in subjects with keratoconus respond to increasing intraocular pressure
Sample Size	230 subjects
Diagnosis and Main Inclusion Criteria	Subjects diagnosed with keratoconus or glaucoma
Control / Comparison	None
Statistical Methodology	Mixed effect models for the comparison between keratoconus and glaucomatous eyes

## **1. Introduction**

This study will be conducted in compliance with the protocol approved by the IRB, GCP guidelines, and applicable NYUMC and federal regulatory requirements.

### **Background**

Glaucoma is a leading cause of blindness worldwide and its prevalence tends to increase (1). Intraocular pressure (IOP) is the primary risk factor for the development and progression of glaucoma, however the mechanisms of damage on tissues of the eye remain unclear (2). The optic nerve head (ONH) was proposed to be a biomechanical structure where the influence of IOP-related connective tissue stress and strain plays a central role in the pathophysiology of glaucoma acting on the ONH connective tissues including the lamina cribrosa (LC), on its axons and on its cellular components (3). Some eyes have characteristics that may render them sensitive to IOP and more likely to develop glaucoma and other eyes present more resilient to IOP and more prone to present with hypertension only (4).

Keratoconus is a frequently occurring asymmetric non-inflammatory disease of the cornea characterized by thinning and ectasia. Its etiology is unknown and it affects mainly the central cornea (5). Histopathological findings of keratoconus explants may explain biomechanical abnormalities such as decreased elastic strength and abnormal shear behavior (6-8). The biomechanical properties of the cornea are currently accessed with the ocular response analyzer (ORA) that is based on a dynamic bidirectional applanation process. This device measures the corneal hysteresis (CH) and the corneal resistance factor (CRF). Studies show that keratoconus has decreased CH and CRF (5, 9).

Optical coherence tomography (OCT) enables tissue pathology to be imaged *in situ* and in real time with a resolution approaching that of conventional histopathology, but without the need for excising and processing specimens. Over the course of the years, we and other groups have demonstrated the excellent diagnostic ability of OCT, and the technology has become the cornerstone of clinical management in ophthalmology worldwide and the number of publications using this technology has soared exponentially in recent years (10, 11). OCT has been approved by the Food and Drug Administration for use in ophthalmology. The device provides accurate and reproducible measurements of tissues of interest in the eye (12). These properties enable improved diagnosis and longitudinal assessment for ocular disease such as glaucoma, age related macular degeneration (AMD), diabetic retinopathy (DR) and macular edema (13-16). Extensive studies have been performed with OCT examining both cross-sectional as well as longitudinal patient populations (17). Our group has published more than 100 peer-reviewed manuscripts focusing on the use of this technology in ocular diseases (18, 19).

Considering that the cornea and the LC are predominantly composed by collagen and elastin fibers, the defective corneal properties might also affect the LC reflected by abnormal response to biomechanical modulation. In the present project, our objective is to evaluate with OCT of the optic nerve head the response to IOP elevation in eyes with keratoconus, with glaucoma and in controls using commercial and prototype ophthalmic OCT imaging instruments in order

## Keratoconus and IOP Elevation Study

to assess the biomechanical properties of the ONH structures including the LC. This project complements our ongoing research on the LC response to pressure modulation in healthy and glaucoma (IRB protocol under review) and in animal models.

### **Study Rationale**

The mechanism by which vision loss in glaucoma occurs is still unknown, but it is clear that increased IOP is a major risk factor. It is also thought that the LC is a site of primary damage during the pathogenesis of the disease. We would like to determine the in-vivo mechanical response to IOP modulation at the level of the ONH and LC. Subjects with keratoconus exhibit abnormal collagen properties that can impair their LC behavior. By evaluating their lamina biomechanical response we can advance our understanding on the role of the lamina in glaucoma pathogenesis. A better understanding of the process will ultimately lead to improved detection and management of glaucoma.

The study design involves a short increase in IOP and imaging with prototype OCT devices to examine the response of the LC to elevated pressure. These devices adhere to all American National Standards Institute safety requirements and do not pose any risk to the participants. The length and magnitude of the pressure elevation in our study design has been previously used, and did not cause any short or long- term damage.

### **2. Study Objectives**

To study the differences in optic nerve microstructure and biomechanical features between keratoconus and glaucomatous eyes. We hypothesize that subjects with keratoconus have an abnormal biomechanical response of the lamina cribrosa in response to IOP modulation.

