### **4. Participant Selection, Enrollment, and Withdrawal**

#### **Study Population**

We aim to enroll 230 subjects including subjects diagnosed with keratoconus or glaucoma (115 in each cohort). There will be no enrollment restrictions based on gender, ethnic origin or HIV status and the study population will reflect the demographics of NYU Department of Ophthalmology.

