## Keratoconus and IOP Elevation Study

As part of the routine examination, pupils will be dilated using dilating drops (tropicamide and/or phenylephrine hydrochloride). As part of routine clinical IOP measurement, numbing drops (proparacaine) will be used. In cases where the clinical evaluation did not include pupil dilation and pupil size prevents ocular imaging, dilating drops might be used for the purpose of imaging in the study.

All procedures will be performed by clinical or research staff.

**Experimental procedure:** The IOP will be measured with the Goldman applanation tonometer, and then the IOP will be increased using an ODM. Proparacaine drops, which are widely used during routine eye examinations, will be used during this procedure to numb the eye while the IOP is measured. ODM is an FDA approved device that allows an increase of force on the eye in a controlled fashion and is routinely used as part of neurophthalmic evaluation. Forces will be imposed on the eye while Goldman tonometry is used to measure the IOP to reach the target IOP between 20-35 mmHg. The procedure will take five minutes.

OCT scanning will be obtained at baseline and with increased IOP. The IOP elevation will last no longer than two minutes, during which scans will be acquired by the imaging device. This stage will take 10 minutes.

The subject will be tested by clinical or research staff under the direct supervision and direction of the principal investigator or co-investigators. All devices in this study are FDA-approved with the exception of the investigational OCT devices and multi-modal adaptive optics system; see Appendix). None of the systems in this study are considered investigational, nor do any of the devices produce harmful radiation.

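### The hypothesis of an abnormal keratoconus lamina response has no normal reference in the plan, and the power statement does not clearly address the keratoconus-glaucoma contrast that the plan can estimate

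*Combined protocol and SAP*

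**What the plan says.** The Study Summary gives the primary objective as "To examine in-vivo how lamina cribrosa in subjects with keratoconus respond to increasing intraocular pressure". The first sentence of section 2 sets out to compare keratoconus with glaucomatous eyes, and the hypothesis follows: "We hypothesize that subjects with keratoconus have an abnormal biomechanical response of the lamina cribrosa in response to IOP modulation".

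On who is studied, the text is not consistent:

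- The Background says the project will evaluate "the response to IOP elevation in eyes with keratoconus, with glaucoma and in controls".
- Section 4, Study Population, plans 230 subjects: "subjects diagnosed with keratoconus or glaucoma (115 in each cohort"). The inclusion criteria require one of these two diagnoses.
- The Study Summary has None in its Control / Comparison row, yet gives the statistical methodology as "Mixed effect models for the comparison between keratoconus and glaucomatous eyes".
- Section 6 divides the data into two groups, keratoconus and glaucoma.
- The end of the Background says the project complements "ongoing research on the LC response to pressure modulation in healthy and glaucoma", which is under a separate IRB protocol. It does not make those eyes a comparator here.

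On size, section 6 anticipates from pilot data a cup-depth increase of about 13 µm on acute pressure elevation. It then claims 80% power at the 5% level, with 230 keratoconus and glaucoma subjects, for a 13 µm difference with an experimental error of 0.07 µm.

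**The concern.** The hypothesis needs a normal reference that the operative plan does not contain. Glaucoma is a reasonable comparator, but it cannot serve as normal. Of the lamina cribrosa (LC) in glaucoma, the Study Rationale says: "It is also thought that the LC is a site of primary damage during the pathogenesis of the disease". If keratoconus and glaucoma eyes respond differently, the data cannot say which group is unusual. If they respond alike, both could be abnormal. Someone following the plan could present a group difference as support for the hypothesis without data that bear on it.

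The keratoconus-glaucoma contrast is the only between-group question the enrolled cohorts can answer, so the reader needs to know how large a difference 115 per cohort can detect. Section 6 does not say so clearly, and its printed inputs do not lead to its printed sample size.

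**Working it through.** **1. What each possible result would show**

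- Non-zero within-eye change in keratoconus: the lamina moves under load. There is no norm to judge it against.
- Keratoconus differs from glaucoma: the groups differ. Either could be the one away from normal.
- Keratoconus equals glaucoma: both could be normal or both abnormal.

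No row confirms or refutes abnormality. The two stated objectives (describe the keratoconus response; compare with glaucoma) can still be met.

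**2. The plan's own power figure**

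Inputs from section 6: difference 13 µm, error 0.07 µm, power 80%, 5% level, 230 subjects. Sidedness is not stated; I take two-sided, so z = 1.960 + 0.842 = 2.802.

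- Two groups: n per group = 2 × (2.802 × 0.07 / 13)² = 0.0005.
- Paired: n = (2.802 × 0.07 / 13)² = 0.0002.

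Both are below 1, and a one-sided test does not change that. The figure of 230 is not reproduced.

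**3. Which inputs would give 230?** (inferences only)

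- *Between groups, 115 each.* SD = 13 / (2.802 × √(2/115)) = 13 / 0.3695 = 35.2 µm gives 80% power for 13 µm.
- *Pooled paired test, 0.07 read as mm (70 µm).* n = (2.802 × 70 / 13)² = 227.6, so 228 by the normal formula; the t-test gives 229.5, so 230. The match is only suggestive, because SDs of 65 and 75 µm give 198 and 263. At 70 µm, power for a 13 µm difference between two groups of 115 is 29%, and about 456 per group would be needed for 80%.

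**4. What 115 per cohort can detect**

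One value per subject, two-sided 5%, 80% power:

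- Detectable difference in change (t-test) = 0.371 SD; the normal formula gives 0.369.
- 95% CI half-width = t(0.975, 228 df) × √(2/115) = 0.26 SD.

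The documents give no usable SD of change, so the SDs below are assumptions:

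| Assumed SD of change (µm) | Detectable difference (µm) | 95% CI half-width (µm) |
|---|---|---|
| 10 | 3.7 | 2.6 |
| 20 | 7.4 | 5.2 |
| 35 | 13.0 | 9.1 |
| 70 | 26.0 | 18.2 |

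The Analysis Methods plan to use both eyes for some subjects. That could improve these figures, but neither the proportion of subjects nor the between-eye correlation is given.

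**The case against.** The strongest reply is that this is largely wording. The hypothesis comes straight after a sentence that sets the contrast as keratoconus against glaucoma, so abnormal may mean only different from glaucoma. Healthy eyes are studied under a companion protocol that may have been meant as the reference. Nothing in the text says a group difference will be reported as abnormality. Much of this stands, and it is why the remedy is mainly textual. But the document neither defines the word that way nor designates the companion data, and the Background's mention of controls leaves the intention open.

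Four stronger readings are tempting, and the documents do not support them:

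- *The study cannot meet its objectives.* It can; only the abnormality claim is out of reach.
- *Cup depth is the wrong outcome for a lamina hypothesis.* The Analysis Methods list cup depth and then treat the listed items as expected LC deformations. What is missing is one named primary outcome.
- *The 13 µm is certainly a within-eye figure, so power between groups is 29%.* The within-eye response is its only stated source, but the power sentence could loosely be read as between groups, and 29% depends on an inferred unit.
- *Unequal pressure rises will distort the group comparison.* Section 5 sets a range: "Goldman tonometry is used to measure the IOP to reach the target IOP between 20-35 mmHg". A group imbalance within it is possible, but nothing in the documents indicates one. The Analysis Methods mention different pressure conditions without listing model covariates, and silence is not exclusion.

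**Conclusion.** The point holds. Within the plan as written, no result can confirm or refute an abnormal keratoconus lamina response, because no normal reference is enrolled, designated or analysed. This rests on the text alone.

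The power statement fails as printed, with a required n below 1 per group against a stated 230, and it does not clearly address the keratoconus-glaucoma difference. For that contrast, 115 per cohort can detect 0.371 SD, assuming a two-sided 5% test, 80% power and one value per subject. Whether that is adequate cannot be judged without the SD of the change: at 35 µm the design has about 80% power for 13 µm, and at 70 µm it has 29%. A reader might infer that the study is underpowered; the documents do not establish that. A keratoconus-glaucoma estimate with its confidence interval would be informative either way.

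**What to change.** 1. **Reconcile the text on controls** across the Study Summary, Background, section 2, Study Population and section 6. With the cohorts as enrolled, restate the hypothesis as a two-sided keratoconus-glaucoma difference in the pressure-induced change, drop the word abnormal, and list glaucoma under Control / Comparison. If the abnormality claim is kept, designate a normal reference: enrolled controls, or named healthy-eye data shown to be comparable in procedure, pressure and OCT device. That choice is the investigators'.
2. **Name one primary outcome** and test the difference as the group-by-pressure term of the mixed model, reporting the estimate with its 95% CI. Say whether cup depth or another of the listed LC deformations is primary, since the power calculation uses cup depth.
3. **Revise the power paragraph in section 6.** State which contrast the 13 µm refers to, correct the value and unit of 0.07, give the pilot SD of the change for the named outcome, and restate power as the keratoconus-glaucoma difference detectable with 115 per cohort (0.371 × SD, one value per subject).
4. **Optional, as a sensitivity analysis only:** include each eye's pressure rise where it was recorded. Section 5 describes tonometry to reach the target but does not place it during scanning, and applanation readings may not be comparable between keratoconus and glaucoma corneas.

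**Cost.** Items 1 to 3 are wording and a recalculation, with no added enrolment if the hypothesis is restated. The downside is that the abnormality claim is given up and the restated detectable difference may look less favourable. If the claim is kept with enrolled controls, before any multiplicity adjustment:

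- 58 controls (58/230 = 25% more subjects) give a detectable keratoconus-control difference of 0.454 SD.
- 115 controls (115/230 = 50% more) give 0.371 SD.
- Splitting about 230 into three cohorts of 77 gives 0.454 SD for every pairwise contrast.

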### **3. Study Design**

This is a prospective, non-randomized, consecutive, experimental study.

### **4. Participant Selection, Enrollment, and Withdrawal**

#### **Study Population**

We aim to enroll 230 subjects including subjects diagnosed with keratoconus or glaucoma (115 in each cohort). There will be no enrollment restrictions based on gender, ethnic origin or HIV status and the study population will reflect the demographics of NYU Department of Ophthalmology.

#### **Inclusion Criteria**

Candidates must meet the following inclusion criteria in order to participate in the study.

- Ages 18 and older
- Ability to provide informed consent and to understand the study procedures

#### ***And have a diagnosis of either:***

##### **Keratoconus:**

- Clinical diagnosis of keratoconus
- Central thinning of the cornea
- Abnormal posterior ectasia.

*Or:*

**Glaucoma:**

- Glaucomatous ONH abnormality: rim thinning, notching, undermining (excavation) or diffuse or localized RNFL defects that are characteristic of glaucoma.
- Two consecutive abnormal SITA standard perimetry tests with GHT outside normal limits.

**Exclusion Criteria**

Candidates that meet any of the exclusion criteria at baseline will be excluded from study participation.

- Media opacity (e.g. lens, vitreous, cornea).
- Strabismus, nystagmus or a condition that would prevent fixation.
- Diabetes with evidence of retinopathy.
- Previous intraocular surgery or ocular trauma.
- Neurological and non-glaucomatous causes for visual field damage.
- Any intraocular non-glaucomatous ocular disorders.

**Participant Recruitment, Screening and Enrollment**

Subjects will be enrolled consecutively from NYU Department of Ophthalmology from the investigator's and the research team's clinics. Eligibility will be determined based on the results of a patient's eye examination, and all qualified subjects will be offered to participate in the study. Study team members will approach participants during their routine examinations at NYU Department of Ophthalmology. To maximize recruitment, eligible subjects may also be contacted via IRB-approved messaging through the NYULH MyChart portal in Epic.

The consent will be obtained after thorough explanation of the study to the participant by the clinician and/or study team member. The participant will be encouraged to ask questions and offered to spend as much time as needed to review the consent with the guidance of the study team member. We will emphasize that participation is voluntary. Documentation of the informed consent process will be used to ensure that the appropriate questions have been asked to the perspective participant. Only study personnel will conduct the consenting process. For candidates who are not fluent in English, NYU translation service will be used to ensure that the candidate fully understands the study and the consent. While the short form will be used with an interpreter, if we encounter a subject who meets inclusion criteria and speaks a language other than English, we will ensure that if more than 10% of prospective subjects per language speak a language other than English, we will amend the submission to include a consent form translated to that particular language.

The site will enroll NYU employees, including those working within the Department of Ophthalmology. Employees listed on the delegation log as study team members will not be enrolled into the research study.

The study assessments/procedures will take place at the NYU Langone Eye Center.

## Keratoconus and IOP Elevation Study

To minimize undue inducement, IRB approved advertisements will be distributed and displayed at IRB approved locations. Interested employees will approach the study team to discuss the study and if they are interested, the informed consent process will take place prior to any study related procedures. The study team member will emphasize that participation is voluntary. The person obtaining consent will also emphasize that the volunteer's decision will not affect their employment within NYU Langone Health and/or NYU School of Medicine.

Participation in the study and data collection will be possible only after subjects have signed consent.

### **Early Withdrawal of Participants**

There are no anticipated circumstances that would lead to discontinuing a subject's participation in this research study.

Subjects may withdraw their consent for participation in this research study at any time. Any identifiable research or medical information recorded for, or resulting from, subject participation in this research study prior to the date that subject formally withdrew consent may continue to be used and disclosed by the investigators for the purposes described above.

### **5. Study Intervention**

Participants will be examined by an ophthalmologist using conventional techniques. The eye examination (which is standard of care) includes recording medical and family history, visual acuity testing, axial length, intraocular pressure and central corneal thickness measurements, slit lamp examination, dilated slit lamp examination with stereo biomicroscopy of the optic nerve head and nerve fiber layer, indirect ophthalmoscopy, and visual field testing. This is followed by imaging of the cornea with Pentacam, hysteresis evaluation with ORA, stereophotography of the optic nerve head, macula and nerve fiber layer optical coherence tomography (OCT) and anterior segment OCT (ASOCT) imaging with FDA approved and non-FDA approved devices (see below). The estimated time for this step is approximately two hours and will occur during a single visit.

The Department of Ophthalmology at NYU includes Pentacam and OCT as part of standard ophthalmic work-up. Every subject with keratoconus routinely undergoes scanning with Pentacam, and they will also have the hysteresis accessed with ORA, both are FDA approved and used as per their approved indication. Subjects with glaucoma routinely undergo imaging with OCT. OCT images will be acquired using commercial OCT instruments (FDA approved devices), and non-commercial instruments that have not been approved by the FDA. More information on the later devices are provided in the appendixes.

These devices are designed using all safety requirements as defined by American National Standards Institute's regulations. The non-FDA approved devices will be used to obtain physiological data, and are non-investigational in the context of this study.

